6 STUDY INTERVENTION(S) OR EXPERIMENTAL MANIPULATION(S)

6.1 STUDY INTERVENTION(S) OR EXPERIMENTAL MANIPULATION(S) ADMINISTRATION

6.1.1 STUDY INTERVENTION OR EXPERIMENTAL MANIPULATION DESCRIPTION

Participants in both experimental conditions will complete an online pre-exposure survey during the baseline phase of the study. Upon completion of the pre-exposure survey, participants assigned to **the radon app condition** will be asked to install the radon app on their smartphones and use the app for three months. App installation will be verified electronically via text message sent to the investigators. To make the informational content of the radon app and EPA brochures equivalent, the informational content in the app condition will be repurposed from EPA brochures used in the brochure condition. Participants in the radon app condition will have the opportunity to order a free radon test kit through the app at any time during the three-month period.

In contrast, individuals assigned to **the brochure condition** will receive three EPA brochures for the three-month period via postal mails. These brochures are (1) Basic radon facts (<https://bit.ly/2S6ryFw>); (2) A citizen's guide to radon (<https://bit.ly/3l3FhcJ>); and (3) Consumer's guide to radon reduction (<https://bit.ly/3ibt83n>). In each mailing, participants will receive a pre-addressed, pre-paid postcard to request a free radon test kit. The postcard will be addressed to a UND address so that we can track the number requested by participants in the brochure condition.

6.1.2 ADMINISTRATION AND/OR DOSING

At the baseline, participants assigned to **the radon app condition** will be asked to install the radon app on their smartphones and use the app for three months. App installation will be verified electronically via text message sent to the investigators. In other words, the intervention is delivered virtually. Participants will not interact with other participants. To make the

informational content of the radon app and EPA brochures equivalent, the informational content in the app condition will be repurposed from EPA brochures used in the brochure condition. Participants in the radon app condition will have the opportunity to order a free radon test kit through the app at any time during the three-month period.

In contrast, individuals assigned to **the brochure condition** will receive three EPA brochures for the three-month period via postal mails. These brochures are (1) Basic radon facts (<https://bit.ly/2S6ryFw>); (2) A citizen's guide to radon (<https://bit.ly/3l3FhcJ>); and (3) Consumer's guide to radon reduction (<https://bit.ly/3ibt83n>). Participants will not interact with other participants. In each mailing, participants will receive a pre-addressed, pre-paid postcard to request a free radon test kit. The postcard will be addressed to a UND address so that we can track the number requested by participants in the brochure condition.

6.2 FIDELITY

6.2.1 INTERVENTIONIST TRAINING AND TRACKING

Ideally, the fidelity of delivery would be monitored by measuring the amount of time persons in the experimental group spent time on the smartphone app. However, this functionality was not developed for financial reasons (the app developer required more money that we had to spend), nor was there any parallel for the comparison group, since there was no way to guarantee that they had indeed read the brochures we sent. However, we did verify the downloading of the app to the experimental group.

With regard to adherence, this was measured indirectly, via the percentage correct of tests of radon knowledge.

6.3 MEASURES TO MINIMIZE BIAS: RANDOMIZATION AND BLINDING

Participants are assigned to either the radon app or brochure condition via the randomization function of Qualtrics. In other words, this trial will utilize the double-blind randomization.

There may be “contamination” of the exposures if participants assigned to the radon app share the app content with classmates assigned to the brochure condition. A consequence of this would be to dilute the effect of group exposure. Participants will be instructed not to share information with others about group assignment. Additionally, we will guard against this via a programming function that permits downloading of the radon app only by individuals assigned to the radon app condition.

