4 STUDY DESIGN

4.1 OVERALL DESIGN

The project begins by comparing the role of the radon app vs. brochures on the percentage of participants that request free test kits and use and return them to the laboratory for analysis and improving knowledge about radon (Phase II).

Experimental design. We designed an online experiment with two experimental conditions—the radon app condition vs. brochure condition—using a pretest-posttest design. Study participants are undergraduates in the Communication Department at UND, indicating that this is a single-site trial. The principal eligibility criterion is that participants own a smartphone. The principal exclusion criterion is previous testing for radon within the past two years.

We consider UND undergraduates to be an appropriate population to test the app for several reasons: (1) ND has the highest residential radon levels in the U.S.²; (2) Our recent review of radon knowledge indicated that most individuals less than 30 years old do not know what radon is¹²; and (3) The age of many undergraduate students is similar to that of first time home-buyers in the U.S.¹³ We will assign recruited participants randomly to one of the two experimental conditions: app use and brochures.

Participants in both experimental conditions will complete an online pre-exposure survey during the baseline phase of the study. Upon completion of the pre-exposure survey, participants assigned to **the radon app condition** will be asked to install the radon app on their smartphones and use the app for three months. App installation will be verified electronically via text message sent to the investigators. To make the informational content of the radon app and EPA brochures equivalent, the informational content in the app condition will be repurposed from EPA brochures used in the brochure condition. Participants in the radon app condition will have the opportunity to order a free radon test kit through the app at any time during the three-month period.

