8 STUDY ASSESSMENTS AND PROCEDURES

8.1 ENDPOINT AND OTHER NON-SAFETY ASSESSMENTS

Once a participant will be directed to the Qualtrics pre-exposure survey link, the consent form will appear on the first page of the survey. Participants will be asked to read it and proceed if they agree. All participants will be asked to answer pre-exposure survey questions measuring key variables, such as radon knowledge, and demographic information to be used in the analyses (e.g., age, gender, home-owner status, smoking status). They will then be randomly assigned to one of the two conditions (via Qualtrics survey's randomization function). Participants assigned to the radon app condition will receive instructions on how to install the app and be instructed to use the app for the next three months. On the other hand, participants assigned to the brochure condition will receive appropriate instructions and be asked to submit both their mailing and email addresses so that they can receive three brochures in the next three months and be contacted for the post-exposure survey. Next, Participants' email and mailing addresses will not be attached to their responses to the pre-exposure survey to protect participants' privacy and confidentiality. Once participants complete the pre-survey, we have the data telling us that: which email address was assigned to which condition, and the timing. After 3 months, we will send the post-exposure survey link to that email address individually. Participants' behaviors,

which are two primary endpoints (i.e., test kit ordering and utilizing behaviors) will be recorded as they become available during the 3-month period.

In summary, participants in both experimental conditions will complete an online pre-exposure survey during the baseline phase of the study and then are randomized to the app or the brochure group. The experimental groups differ only in the means by which information is conveyed, not in the nature of the information. Participants in both conditions will have the opportunity to order a free radon test kit at any time during the three-month period.

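### Section 6.3 calls the trial double-blind, but the plan masks neither participants nor study staff, and the self-completed knowledge score is the outcome mainly exposed

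*Combined protocol and SAP*

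**What the plan says.** Section 6.3 is the only place where the documents address blinding. It first describes allocation: "Participants are assigned to either the radon app or brochure condition via the randomization function of Qualtrics". The next sentence restates this as blinding: "In other words, this trial will utilize the double-blind randomization". It does not say which parties are masked, or how.

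Other sections describe what each side sees:

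- App participants "will be asked to install the radon app on their smartphones and use the app for three months" (Section 6.1.2).
- Brochure participants "will receive three EPA brochures for the three-month period via postal mails" (Section 6.1.2).
- On the staff side, "App installation will be verified electronically via text message sent to the investigators" (Section 4.1).
- Once the pre-exposure survey is complete, the team has data showing "which email address was assigned to which condition, and the timing" (Section 8.1). It then sends the three-month survey link to each address.

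**The concern.** Random allocation, concealment of the next allocation and masking after allocation are three separate protections. Section 6.3 moves from the first to the third as if they were the same. A report that repeats the term would claim a safeguard that the design cannot provide, since an app and a posted brochure cannot be made to look alike.

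What is at stake is how the results are read, above all for radon knowledge. That score comes from a true/false test that participants complete online, with no supervision described, after three months of knowing which arm they are in. Effort or expectation could differ between arms for reasons unrelated to the information delivered. A reader who takes the blinding statement at face value has less reason to allow for this.

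**Working it through.** The point rests on no figure, and blinding does not enter the sample-size statement in Section 9.2. The check compares sections.

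**1. Does the stated basis support the claim?** The only basis given is the Qualtrics randomiser. It removes human choice of the arm. It does nothing to hide the arm afterwards, so the claim does not follow.

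**2. Are participants masked?** No. Section 8.1 gives each arm different instructions: "Participants assigned to the radon app condition will receive instructions on how to install the app", while the brochure arm is asked for a mailing address. Section 6.3 itself assumes that participants know their group, because "Participants will be instructed not to share information with others about group assignment".

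**3. Are study staff masked?** No, in either arm. Installation texts reveal the app arm, and Section 6.2.1 confirms that downloads were verified. The list linking email address to condition covers both arms. Section 8.1 adds that addresses are kept apart from the pre-exposure answers, so staff know who is in which arm, but this does not show that they could influence the answers.

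**4. Is anyone else masked?** Nothing is said about the laboratory or the analyst. Laboratory staff may in practice be unaware of the arm, but the plan does not state it.

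**5. How exposed is each endpoint?**

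| Endpoint | How it is obtained | Exposure to knowledge of the arm |
|---|---|---|
| Kits requested (primary) | Count, through the app or by postcard | Limited: no assessor judgement |
| Kits returned to the laboratory (primary) | Count | Limited: no assessor judgement |
| Radon knowledge (secondary) | 20 self-completed items, recoded 1 or 0 by key (Section 9.4.3) | Main exposure: scoring is objective, but effort is the participant's own |

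This ordering is a judgement from how each outcome arises, not an estimate.

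**6. Is baseline knowledge also exposed?** Possibly. Section 8.1 places randomisation after the pre-exposure questions. Section 5.5 has app participants install and log in, and brochure participants give an address, before they complete that survey. If Section 5.5 describes what was done, baseline answers too could be given with the arm known. The two sections need reconciling.

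**7. Could the main tests be run on coded arms?** Yes, if direction is handled. The tests in Sections 9.4.2 and 9.4.3 are one-sided towards the app. For coded arms A and B, Z = (pA − pB)/SE. The one-sided p-value is 1 − Φ(Z) if A is the app and Φ(Z) if B is the app. Both can be computed before unmasking, and the one that applies is then fixed by the hypothesis, not by the result. The same holds for the knowledge t-test, with the t distribution in place of Φ. The Section 9.4.7 model cannot be coded in this way: it adjusts for time on the app, which only one arm can have and which would reveal the code.

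**The case against.** The strongest reply is that the phrase is a misnomer. It directly follows the mention of the randomiser and probably means automated allocation that neither side controls. The synopsis, the overall design and the design rationale do not use the term, no analysis depends on masking, and the contrast between app and mailed brochures is plain throughout. This is a fair reading of intent. It does not rescue the sentence, which stands under a heading on bias and blinding and has an established meaning that the design does not meet.

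A reader might go further and infer that unmasked staff could bias the primary endpoints through postcards, reminders or discontinuation decisions. The documents do not support that:

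- Both primary endpoints are counts.
- Reminders follow one rule for both arms and concern the survey, not kit ordering or return (Section 5.5).
- Participants who stop the intervention remain in later assessments (Section 7.1).
- The analysis population is everyone randomised (Section 9.3).
- Who handles the postcards is not stated, only that they go to a university address.

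One narrow route remains open. Section 7.2 lets an investigator withdraw a participant for non-compliance, which could affect who supplies three-month knowledge data. Nothing shows that this would differ by arm.

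It is also true that participants cannot be masked to app versus paper. The fault lies in the description, not in the choice of an open-label design.

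**Conclusion.** The point holds as a correction to a stated property of the trial. Section 6.3 claims double-blinding, while the plan's own procedures leave participants and study staff aware of the arm and describe masking for nobody. The size of any resulting bias cannot be derived from the documents. It falls mainly on the secondary knowledge comparison and is limited for the kit counts.

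Two stronger inferences should be resisted. The documents do not show that randomisation failed or that allocation could be predicted. Nor do they show a staff-driven bias in the primary endpoints. No endpoint, estimate or sample size changes.

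The verdict assumes that no masking arrangement exists outside the text available. The ranking of exposure assumes that the knowledge survey is taken unsupervised, as an emailed survey link suggests.

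**What to change.** Replace the sentence in Section 6.3 with: *Open-label trial; arms are allocated at random by the Qualtrics randomiser and cannot be foreseen before assignment; participants and study staff are not masked.* If the laboratory or the analyst is in fact masked, say so. Report awareness of the assigned arm as a limitation of the knowledge comparison, and reconcile Sections 5.5 and 8.1 on whether the baseline survey precedes assignment.

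Optionally, and only if the data have not yet been analysed by arm, run the primary Z tests and the knowledge t-test on arms coded A and B. Compute both one-sided directions, then unmask and keep the direction that favours the app. Run the Section 9.4.7 model after unmasking.

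The required change costs one sentence in the protocol and one in the report. The optional step adds a little analysis work. It also needs someone other than the analyst to hold the code, and the documents do not say whether such a person is available.

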6.4 STUDY INTERVENTION/EXPERIMENTAL MANIPULATION ADHERENCE

Participants' adherence with study procedures for the radon app condition will be tracked based on the back-end data provided by the app development company, Triad Interactive Media. A complete adherence is not expected, however, because participants were asked to use the app occasionally as they would do for other apps. Participants' adherence with study procedures for the brochure condition will be tracked based on the number of returned postal mails. A 100%

delivery of postal mails is not expected, however, because delivery failure reflects the real-life situations participants would face in other situations.

6.5 CONCOMITANT THERAPY

N/A

6.5.1 RESCUE THERAPY

N/A

7 STUDY INTERVENTION/EXPERIMENTAL MANIPULATION DISCONTINUATION AND PARTICIPANT DISCONTINUATION/WITHDRAWAL

7.1 DISCONTINUATION OF STUDY INTERVENTION/EXPERIMENTAL MANIPULATION

When a subject discontinues from accessing the radon app or receiving printed brochures, but not from the study, remaining study procedures will be completed as indicated by the study protocol. If a clinically significant finding is identified (including, but not limited to changes from baseline) after enrollment, the investigator or qualified designee will determine if any change in participant management is needed. Any new clinically relevant finding will be reported as an adverse event (AE).

The data to be collected at the time of study intervention discontinuation will include the following:

- The reason(s) for discontinuing the participant from the intervention, and methods for determining the need to discontinue.
- If the participant is due to complete assessments within 2 weeks of being discontinued from the study intervention, those assessments will be administered at the time of discontinuation; if the next scheduled assessments are more than 2 weeks from the discontinuation date, the discontinued participant will wait for the next scheduled assessment. Thereafter, the participant will be included in all future scheduled assessments, even though not participating in the intervention.

7.2 PARTICIPANT DISCONTINUATION/WITHDRAWAL FROM THE STUDY

Participants are free to withdraw from participation in the study at any time upon request.

An investigator may discontinue a participant from the study for the following reasons:

- Significant study intervention non-compliance, unless varying compliance is an aspect of the study objectives
- Lost-to-follow up; unable to contact subject (see **Section 7.3, Lost to Follow-Up**)

- Any event or medical condition or situation occurs such that continued collection of follow-up study data would not be in the best interest of the participant or might require an additional treatment that would confound the interpretation of the study
- The participant meets an exclusion criterion (either newly developed or not previously recognized) that precludes further study participation

The reason for participant discontinuation or withdrawal from the study will be recorded by the PI. Subjects who read the informed consent form, and are randomized and receive the study intervention, and subsequently withdraw, or are discontinued from the study, will not be replaced.

7.3 LOST TO FOLLOW-UP

A participant will be considered lost to follow-up if he or she fails to complete the post-exposure survey and study staff are unable to contact the participant after at least 2 attempts.

The following actions must be taken if a participant fails to complete the post-exposure survey:

- The site will attempt to contact the participant, counsel the participant on the importance of maintaining the assigned visit schedule and ascertain if the participant wishes to and/or should continue in the study.
- Before a participant is deemed lost to follow-up, the investigator or designee will make every effort to regain contact with the participant via a reminder email. These contact attempts will be documented in the participant's medical record or study file.
- Should the participant continue to be unreachable, he or she will be considered to have withdrawn from the study with a primary reason of lost to follow-up.

8 STUDY ASSESSMENTS AND PROCEDURES

8.1 ENDPOINT AND OTHER NON-SAFETY ASSESSMENTS

Once a participant will be directed to the Qualtrics pre-exposure survey link, the consent form will appear on the first page of the survey. Participants will be asked to read it and proceed if they agree. All participants will be asked to answer pre-exposure survey questions measuring key variables, such as radon knowledge, and demographic information to be used in the analyses (e.g., age, gender, home-owner status, smoking status). They will then be randomly assigned to one of the two conditions (via Qualtrics survey's randomization function). Participants assigned to the radon app condition will receive instructions on how to install the app and be instructed to use the app for the next three months. On the other hand, participants assigned to the brochure condition will receive appropriate instructions and be asked to submit both their mailing and email addresses so that they can receive three brochures in the next three months and be contacted for the post-exposure survey. Next, Participants' email and mailing addresses will not be attached to their responses to the pre-exposure survey to protect participants' privacy and confidentiality. Once participants complete the pre-survey, we have the data telling us that: which email address was assigned to which condition, and the timing. After 3 months, we will send the post-exposure survey link to that email address individually. Participants' behaviors,

which are two primary endpoints (i.e., test kit ordering and utilizing behaviors) will be recorded as they become available during the 3-month period.

In summary, participants in both experimental conditions will complete an online pre-exposure survey during the baseline phase of the study and then are randomized to the app or the brochure group. The experimental groups differ only in the means by which information is conveyed, not in the nature of the information. Participants in both conditions will have the opportunity to order a free radon test kit at any time during the three-month period.

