5.5 STRATEGIES FOR RECRUITMENT AND RETENTION

COMM 110 and 102 students were invited to participate in the study. In the communication department, students enrolled in COMM 102 are required to complete the 2-hour research participation requirement. The participation in both pre- and post-exposure surveys in each experiment would allow them to meet an hour of participation requirement. For COMM 110, students receive extra .5% in their final grade per an half-hour research participation, and they are allowed to earn up to extra 2% (i.e., 2-hour research participation), according to COMM 110's extra credit policy. The participation in both pre- and post-exposure surveys in each experiment would allow them to earn extra 1% for their final grade (i.e., one-hour research participation).

Approximately 200 students are enrolled in COMM 102 each semester, and about 600 students are enrolled in COMM 110 each semester. They are included in the Communication Department's SONA website, which is the research participation pool website run by the department. Once the study is available on SONA website, students receive an email from SONA, and if they agree to participate in the study, they will sign up for the study on SONA website. They will be able to sign up for a 30-minute time slot for the pre-exposure survey session. Those who complete the pre-exposure survey will receive the same recruitment email encouraging them to sign up for another 30-minute time slot for their post-exposure survey session. This method was deemed appropriate to reach this target study population because they were familiar with the SONA system overall and receiving study notification emails.

Participants who agree to be in the study will receive a pre-exposure online survey link. Once they click on the link, they will be asked to read the consent form first. Screening questions will appear on the next page. Those who met the eligibility criteria were then able to proceed with the questionnaire and randomized. Those who did not meet the eligibility criteria were directed to the end of the survey.

Half of the participants assigned to the radon app condition will be asked to provide their Twitter information. If participants don't have a Twitter ID, they will be asked to create a new one prior to

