completing the pre-exposure survey. Once the app is installed in participants' own phones and they successfully log in through their Twitter credentials, they will be asked to keep the app on their phone for three months with the notification setting "on". After all these steps are completed, they will be asked to complete the pre-exposure survey. The radon app can be accessed via computer or smartphone: <https://radon-production.herokuapp.com/>

The other half of the participants assigned to the brochure condition will be asked to provide the mailing address prior to completing the pre-exposure survey so that they can receive EPA brochures in the next 3 months via postal mail. Once this step is completed, they will be asked to complete the pre-exposure survey. During the 3-month period, participants assigned to the radon app condition will receive the radon educational materials via the app. Materials include the informational content repurposed from EPA brochures and radon-education Tweets using hashtags, such as #radon, #lungcancer, #healthylungs, and #radonawareness. The app uses the Twitter's mechanism so that's why participants need to use their Twitter credentials to login, and those hashtags used in Tweets are automatically detected by the app, and will be populated in the app. While keeping the app for three months, if participants would like to test their homes for radon levels, as education materials they will be exposed to encourage to do so, they can request a free radon kit through the app. They will be asked to enter their mailing address, email, and phone number so that the kit will be delivered to their home address. Although the app would collect such personal information, this is only to provide them with the free radon kit, and such information won't be attached to their any survey responses. On the other hand, participants assigned to the brochure condition will receive a total of three EPA brochures, with each one being delivered once a month. In each mailing, participants will receive a pre-addressed, pre-paid postcard to request a free radon test kit. The postcard will be addressed to a UND address so that we can track the number requested by participants in the brochure condition.

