Participants who completed the pre-exposure survey then received an email reminder including the link for the post-exposure survey three months after the completion of their pre-exposure survey. Participants who did not complete the post-exposure survey two weeks after the initial email received a reminder email.

A sample size of at least 100 students in each group was determined to have a power of .8 to .9 to detect differences in proportions of at least 20%, Chi-square values of five or more with one or two degrees of freedom, mean differences of at least 0.3, and odds ratios greater than three in logistic regression.

Participant incentives:

Students who were enrolled in COMM 110 class received 0.5 extra course credit point for the completion of pre-exposure survey, which was equivalent to the half-hour research participation. If they completed the second and final session (i.e., post-exposure survey), they received additional 0.5 extra credit point.

Students who were enrolled in COMM 102 class met the half-hour research participation requirement for completing the pre-exposure survey. If they completed the second and final session (i.e., post-exposure survey), they met additional half-hour research participation requirement.

In addition to extra credit or meeting the research requirement, students received a \$10 gift card for the completion of pre-exposure survey. If they complete the second and final session (i.e., post-exposure survey), they received another \$15 gift card.

All students included in the Comm department's SONA research pool are 110 and 102 students, and they are taught by GTAs (110) and a designated instructor (102). The PI has never taught 102 or 110 courses, and will not do so. But in case any of PI's students are invited to the study, they will be given an option to complete an alternative task as a way to avoid coercion or undue influence.

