9.4.3 ANALYSIS OF THE SECONDARY ENDPOINT(S)

Secondary endpoints:

Effectiveness of the radon app vs. brochure at 3 months re: changes in radon knowledge, as measured by the number of correct responses to a series of 20 true/false questions (e.g., "The EPA recommends that homes with 4 picocuries per liter (pCi/L) or more of radon should be fixed.").

Radon knowledge will be measured by the number of accurate responses to 20 True-False statements in T1 (baseline) and T2 (at 3 months).¹¹ The response options will be: "true," "false," and "I don't know." Participants' responses to each statement will then be re-coded to 1 ("correct") or 0 ("incorrect" or "I don't know"). After that, two radon knowledge index variables (continuous) will be created by summing participants' responses to each statement in T1 (baseline) and T2 (at 3 months). Lower numbers on index variables indicate a low level of knowledge, whereas higher numbers indicate greater knowledge.

H₀: There will be no changes in radon knowledge among those assigned to the radon app condition and those assigned to the brochure condition. **H₁**: There will be more positive changes in radon knowledge among participants assigned to the radon app condition. **Statistical test**: Differences in radon knowledge between the two groups will be tested with directional, independent t-tests, with SAS.

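### As described, the 3-month knowledge test is an unsupervised emailed survey with no from-memory instruction, so the score may mix look-up with retained knowledge, possibly unequally by arm

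*Combined protocol and SAP*

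**What the plan says.** All references are to the combined protocol and SAP.

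- **Delivery of the test.** Section 8.1: "After 3 months, we will send the post-exposure survey link to that email address individually". Section 5.5 agrees that participants "received an email reminder including the link for the post-exposure survey three months after the completion of their pre-exposure survey", with a further reminder two weeks later to those who have not responded. Section 5.5 also has participants "sign up for another 30-minute time slot for their post-exposure survey session". No proctor, venue, timer or browser restriction is described.
- **Scoring.** Section 9.4.3 sums correct answers to 20 items at T1 (baseline) and T2 (three months). Wrong and don't-know answers score 0. The arms are compared with a one-sided independent t-test whose alternative favours the app.
- **Materials.** In the app arm, "they will be asked to keep the app on their phone for three months", and "The radon app can be accessed via computer or smartphone" (both Section 5.5). The brochure arm is mailed three printed brochures, one a month. Section 4.1 says the app content is drawn from those same brochures. No step closes app access or collects brochures before the test.
- **Silence.** Neither 8.1 nor 9.4.3 asks participants to answer without sources, records whether they used any, or plans an analysis for it.
- **Role of the score.** Section 3 makes knowledge the secondary endpoint and names it as a possible mediator. Section 4.1 lists it among the primary endpoints. Section 6.2.1 uses it as an indirect measure of adherence.

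**The concern.** The objective is to compare how far the two media increase radon knowledge. Items with fixed factual answers, taken online without supervision, can be answered by looking them up. A correct answer then shows that a source was within reach, not that anything was learned.

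If look-up is equally common and equally helpful in both arms, the comparison of means stays fair, but the score is no longer a clean measure of what the objective names. If it differs by arm, the difference between arms includes a component that is not learning. A difference is conceivable because the two media are not equally easy to reach during an online survey: one opens on a phone or computer, the other is paper that arrived over the preceding months.

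The information needed to judge this has to be collected during the survey. It cannot be reconstructed at analysis.

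**Working it through.** **1. The plan's own figure.** The plan gives no figure for look-up. The only stated figure that touches the knowledge score is in Section 9.2: power of 0.8 to 0.9 for a mean difference of 0.3 with 100 per group. Read as 0.3 SD in a one-sided 5% independent test, power = Φ(0.3/√(2/100) − 1.645) = Φ(2.121 − 1.645) = 0.68. Read as 0.3 raw items, power of 0.8 to 0.9 needs an SD of about 0.85 to 0.72 items. Units, SD and alpha are not stated, so the figure can be neither confirmed nor refuted. It is not in dispute here; it matters only because no SD for the knowledge score can be taken from it.

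**2. Inputs for an illustration.**
- From the plan: 100 per arm (9.2), one-sided independent t-test and 0-20 score (9.4.3).
- Assumed: alpha 5% one-sided; SD 3 to 4 items; no true difference; the look-up difference between arms *d*; the items gained by each person who looks up *g*. The documents give none of these.

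**3. Formula.** Shift in the mean difference = d × g. Standard error = SD × √(2/100), which is 0.424 for SD 3 and 0.566 for SD 4. One-sided rejection rate = Φ(shift/SE − 1.645).

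Example: d = 5 points, g = 4 items, shift 0.05 × 4 = 0.2. With SD 3: Φ(0.2/0.424 − 1.645) = Φ(−1.17) = 0.120.

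| Look-up more common in | Shift (items) | SD 3 | SD 4 |
|---|---|---|---|
| neither arm | 0 | 0.050 | 0.050 |
| app arm, 5 points × 4 items | +0.2 | 0.120 | 0.098 |
| app arm, 10 points × 3 items | +0.3 | 0.174 | 0.133 |
| brochure arm, 5 points × 4 items | −0.2 | 0.017 | 0.023 |
| brochure arm, 10 points × 3 items | −0.3 | 0.009 | 0.015 |

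The noncentral t with 198 degrees of freedom agrees to about 0.001 for the app-arm rows. Over a wider grid (SD 2 to 4, gain 2 to 6 items), a 5-point app-arm excess gives 0.07 to 0.28, a 10-point app-arm excess gives 0.10 to 0.68, and a 10-point brochure-arm excess stays below 0.03. The result is driven almost wholly by the assumed inputs.

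**4. Baseline order.** Section 5.5 has the app installed and logged in before the pre-exposure survey is completed. Sections 6.1.1 and 8.1 put installation after it. Brochures arrive by post later in either case. If 5.5 is followed, only the app arm has study material at T1. For a change score the shift becomes (d × g at T2) − (d × g at T1): with an app-arm excess of 0.3 items at both times, 0.3 − 0.3 = 0, and a larger excess at T1 would work against the app.

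**The case against.** A reader might infer that the procedure favours the app and inflates the false-positive rate to 10-17%. The documents do not support that, for these reasons:

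- Both arms receive the same survey by the same route. Brochure participants may still hold the same content on paper, and a web search is open to everyone. App access also needs a Twitter login, so it is not clearly easier than a search.
- That the app is still in hand at the test is an inference. The request to keep it runs for three months and the link goes out at three months; what happens afterwards is not stated.
- Credit and gift cards reward completion, not score (Section 5.5), so no stated incentive for look-up exists.
- Under the Section 5.5 order of installation, look-up at T1 could shrink the app arm's change.
- The 10-17% range is arithmetically right but uses only app-favouring assumptions; mirrored assumptions give about 1-2%.

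A reader might also take the score to be the planned mediator of kit ordering. Section 3 says only that it might serve as one, and no mediation analysis is specified.

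Finally, the questionnaire itself is not reproduced, so on-screen instructions cannot be checked. The finding is limited to what the protocol text contains.

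All of this stands against a claim about direction or size. It leaves intact that the protocol describes an open-book test for an endpoint called knowledge and collects nothing that would show whether look-up was balanced.

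**Conclusion.** The concern holds in a limited form. As written, the plan cannot separate retained knowledge from access to materials at three months, and it cannot show whether access was used equally in the two arms. Direction and size are unknown. With equal look-up the one-sided error remains 5%; an app-arm excess would raise it and a brochure-arm excess would lower it. The figures above only illustrate how sensitive the test is, under an assumed alpha, SD, look-up difference and gain.

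The scope is the knowledge score and its use as an adherence proxy. The kit-request and kit-return endpoints are unaffected. The change is worth making because it is cheap and the missing information cannot be recovered later, not because a bias has been shown.

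**What to change.** In Sections 8.1 and 9.4.3:

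1. Before the 20 items, in both arms and at both T1 and T2, place the same instruction: answer from memory; do not open the app, the brochures or the internet; choose the don't-know option if unsure. That option already exists and is scored 0.
2. After the items, ask one question on whether any source was consulted. Report the answers by arm.
3. Keep the ITT comparison of all randomised participants as the main analysis. If reported consultation differs by arm, interpret the knowledge result cautiously and show a labelled sensitivity range for those who consulted a source, for example from T2 as observed to T2 set equal to T1. The second end is an extreme bound, not an estimate: it assumes these participants learned nothing and conditions on a report made after randomisation. Nobody is dropped.
4. Reconcile Section 5.5 with Sections 6.1.1 and 8.1 on whether the app is installed before or after the pre-exposure survey, since app access at T1 affects the change score.

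**Cost.** Two short additions to an existing online survey, a minor notification to the ethics board and one extra analysis. Consultation is self-reported, so the check is partial. Parts of the protocol are in the past tense; if the surveys have already been completed, items 1 and 2 are no longer possible and the point should be reported as a limitation of the knowledge endpoint.
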